7.2. Protocol Deviations

Subject-specific protocol deviations will be summarized by the reason for the deviation, the deviation category, treatment group, disease severity and (separately) site for all subjects (Table 12 and Table 13). All subject-specific protocol deviations and non-subject specific protocol deviations will be included in listings (Listing 3 and Listing 4).

8. EFFICACY EVALUATION

8.1. Primary Efficacy Analysis

8.1.1. Primary Analyses

All the summaries described in this section will be generated for both the early and the full analysis sets.

The primary analysis uses the stratified log rank test to compare treatment to control through Day 29 with respect to time to recovery, as defined in Section 3.3. Stratification is based on mild/moderate versus severe disease at baseline. As noted in Section 3.3, all deaths within 29 days will be considered censored at Day 29 with respect to time to recovery. Conceptually, a death corresponds to an infinite time to recovery, but censoring at any time greater than or equal to Day 29 gives the same answer as censoring at Day 29; both correspond to giving deaths the worst rank.

Let MM and S denote the Mild/Moderate and Severe subgroups, respectively. The z-score associated with the stratified log rank test is

$$Z = \frac{\sum_{MM}(O_i - E_i) + \sum_S(O_i - E_i)}{\sqrt{\sum_{MM} V_i + \sum_S V_i}}$$

The sums are over recovery times t_i in the mild/moderate and severe subgroups, O_i is the number of treatment arm participants recovering at time t_i , and E_i and V_i are the null expected value and variance of the number of treatment recoveries calculated using the hypergeometric distribution. Specifically, if n_{Ti} and n_{Ci} denote the numbers of patients 'at risk' in the two arms in a given stratum at t_i , and r_i is the total number of recoveries at t_i , then $E_i = r_i n_{Ti} / (n_{Ti} + n_{Ci})$ and $V_i = r_i (n_i - r_i) n_{Ti} n_{Ci} / [n_i^2 (n_i - 1)]$, where $n_i = n_{Ti} + n_{Ci}$. The O_i , E_i , and V_i are computed separately within the mild/moderate and severe strata.

As noted in Section 6.6.2, to maintain an overall two-sided type-I error rate of 0.05, the Lan-DeMets spending function analog of the O'Brien-Fleming boundary will be used to derive the cumulative error spending and boundaries for the interim analyses.

The log rank test will be performed using the pseudocode provided in Section 6.1. The following pseudocode can be used to compute the bounds for the final analyses and compare to the calculated log-rank statistic. The `Boundaries` dataset will contain the updated boundaries calculated from the interim analyses using the actual information levels observed at the interim analyses.

```
data Parms_LogR;
  set logrankp(rename=(Statistic=Estimate));
  if Variable='TreatmentVariable';
  _Scale_='Score';
  _Stage_= AnalysisNumber;
  keep Variable _Scale_ _Stage_ StdErr Estimate;
run;

proc seqtest Boundary=Boundaries
  Parms (Testvar=TreatmentVariable)=Parms_LogR
```

```
inftoadj=prop  
boundaryscale=score  
;  
ods output Test=FinalResults ParameterEstimates = LogHRest;  
run;
```

If the trial is stopped at the interim analysis, then to derive the p-value, hazard ratio estimate, and confidence interval for the early and final analysis sets, stage-wise ordering of the sample space will be used [5]. The resulting p-value, median unbiased estimate, and confidence interval will be presented in the final report. If the trial is not stopped early, then the fixed sample estimates of the statistics using an alpha level of 5% will be computed and reported for the early and final analysis sets. The SAS pseudocode above provides estimates for the log hazard ratio and so the estimates will be exponentiated and reported.

The primary analysis will be performed in the ITT analysis population. The treatment hazard ratio estimate and confidence interval and p-value from the stratified log rank test will be presented (Table 14). The median time to event and 95% confidence interval will be summarized by treatment arm and disease severity. In addition, stratum-specific estimates of the treatment hazard ratio from Cox models run within each of the disease severity strata will be presented. Kaplan-Meier curves for each treatment arm will be presented, supplemented with the hazard ratio estimate, p-value, and the number of subjects at risk in each arm and severity stratum at Days 1, 3, 5, 7, 11, 15, 22, and 29 (Figure 2).

Subject listings of the ordinal scale results by day will be generated (Listing 5).

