6. GENERAL STATISTICAL CONSIDERATIONS

6.1. General Principles

This is a double-blind, placebo controlled randomized trial with a two-sided type I error rate of 0.05. Secondary hypotheses have been ordered according to relative importance. These will be described according to the appropriate summary statistics, e.g.

- Percentages/proportions/odds ratios for categorical data. For tabular summaries of percentages/proportions, the denominator (e.g. number of subjects with non-missing data) will be displayed.
- Means, median, and range for continuous data, median for time-to-event data.

Confidence intervals will be generated; for the primary analysis, the confidence level will take into account the group-sequential design of the trial (see Section 6.6 and Section 8.1) whereas 95% confidence intervals will be generated for secondary and exploratory outcomes. For hazard ratio and odds ratio estimates, Wald confidence intervals will be used. For other efficacy outcomes, Wilson or Score confidence intervals will be used. For safety outcomes, exact (e.g. Clopper-Pearson) confidence intervals will be used.

When calculating treatment effects (e.g. differences, hazard ratios, odds ratios) and when using treatment arm as a covariate in regression modeling, the placebo arm will be used as the reference group. For regression modeling that uses strata variables defined in Section 6.4, the first stratum listed for each variable in that section will be used as the reference group.

For the final time-to-event analyses, the following SAS pseudocode will be used to perform stratified analyses to generate stratum-specific median time to event estimates and confidence intervals, stratum-specific Kaplan-Meier curves, and to perform the log-rank test. For any unstratified analyses, code can be used after the removal of the `strata ... ;` line.

```
proc lifetest data=dataset plots=(s);
  time TimeVariable * CensorVariable(1);
  strata StrataVariable;
  test TreatmentVariable;
run;
```

Note that the interim efficacy analyses will be performed using R. For all interim and final analyses, the software used will calculate the log rank statistic using the formula in Section 8.1.1.

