6.2.3. Final Analyses

After the DSMB meeting on April 27, 2020, the interim results were provided to the sponsor and the interim analyses were performed again on an April 28, 2020 database freeze (unlocked dataset). The results of these analyses were made public on April 29, 2020. Subsequent to this, the plan for the final analyses (and corresponding datasets) was modified to the following:

- A preliminary analysis of the primary, key secondary, and major safety outcomes will be performed on unlocked, partially clean version of data and events that occurred up to April 28, 2020. This preliminary analysis dataset was used for the analyses and summaries included in the “Remdesivir for the Treatment of Covid-19 – Preliminary Report” article published in The New England Journal of Medicine on May 22, 2020 (DOI: 10.1056/NEJMoa2007764) and will be used for the preliminary report, whose summaries will coincide with the summaries provided in the article. This dataset will not be used for any further analyses apart from the preliminary report.
- A fully cleaned and locked version of data and events that occurred up to April 28, 2020 will be denoted as the “early analysis set”. Section 7, Section 8, and Section 9 denote which summaries will be provided as part of this report, but will focus largely on primary outcome, key secondary outcome, and mortality.

- The final analyses of all outcomes and planned summaries/listings will be performed on the final full locked database and provided in an addendum to the final report. This is the fully cleaned and locked version of all data and events that occurred at any time during this trial and will be denoted as the “full analysis dataset”.

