6.6.2. Interim Efficacy Review

Interim efficacy analyses will be conducted after at approximately 50% of total information. The information fraction at an interim analysis will be computed as $t = r/400$, where r is the number of recoveries by the time of the data freeze date for the interim analysis. The Lan-DeMets spending function analog of the O'Brien-Fleming boundary will be used to monitor the

primary endpoint using an overall two-sided type-I error rate of 0.05. Specifically, two one sided boundaries are constructed at level 0.025 using the spending function

$$\alpha^*(t) = 2[1 - \Phi\{2.241/t^{\frac{1}{2}}\}],$$

where Φ is the standard normal distribution function. Lan-DeMets software from the University of Wisconsin, now available in the R package 'lrbounds', will be used to calculate boundaries.

Conditional power will be presented as an additional guide to the DSMB. Conditional power allows computation of the probability of obtaining a statistically significant result by the end of the trial given the data accumulated thus far, incorporating and assuming a hypothesized treatment effect (e.g., the treatment effect assumed for sample size determination) thereafter. If conditional power is less than 20% under the original trial assumptions, consideration should be given to stopping the trial.

The unblinded statistical team will prepare these closed reports for DSMB review and recommendations. Analyses will be presented with blinded codes for treatment arms to protect against the possibility that the DSMB report may fall into the wrong hands. A DSMB charter will further describe procedures and membership. An additional document on statistical issues related to monitoring will be provided to the DSMB prior to interim analyses.

Section 6.2.3 describes the plan for the final analyses of the early and final analysis sets.

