6.8. Multiple Comparisons/Multiplicity

There is only one primary outcome measure. The study utilizes a group-sequential design to control the overall type I error rate while allowing for formal interim analyses of the primary outcome measure (as described in Section 6.6 and Section 8.1). There is no planned adjustment for multiple comparisons in any secondary or exploratory analyses.

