		Mild-Moderate (N=X)		Severe (N=X)		Mild-Moderate (N=X)		Severe (N=X)		Mild-Moderate (N=X)		Severe (N=X)	
		# of Subj.	# of Dev.	# of Subj.	# of Dev.	# of Subj.	# of Dev.	# of Subj.	# of Dev.	# of Subj.	# of Dev.	# of Subj.	# of Dev.
	Required procedure done incorrectly	x	x	x	x	x	x	x	x	x	x	x	x
	Study product temperature excursion	x	x	x	x	x	x	x	x	x	x	x	x
	Specimen temperature excursion	x	x	x	x	x	x	x	x	x	x	x	x
	Other	x	x	x	x	x	x	x	x	x	x	x	x
Treatment administration	Any type	x	x	x	x	x	x	x	x	x	x	x	x
	Required procedure done incorrectly	x	x	x	x	x	x	x	x	x	x	x	x
	Study product temperature excursion	x	x	x	x	x	x	x	x	x	x	x	x
	Other	x	x	x	x	x	x	x	x	x	x	x	x
Blinding policy/procedure	Any type	x	x	x	x	x	x	x	x	x	x	x	x
	Treatment unblinded	x	x	x	x	x	x	x	x	x	x	x	x
	Other	x	x	x	x	x	x	x	x	x	x	x	x

N = number of subjects enrolled

Tables with similar format:

Table 13: Distribution of Protocol Deviations by Category, Type, and Site

Table 14: Time to Recovery by Treatment Group and Disease Severity

Analysis Population	Treatment Group	Disease Severity	n	Median Time to Recovery		HR		P-value
				Estimate	95% CI	Estimate	95% CI	
ITT Population	Remdesivir (N=X)	Mild/Moderate	x	x.x	x.x, x.x	x.x	x.x, x.x	0.xxx
	Placebo (N=X)		x	x.x	x.x, x.x			
	Remdesivir (N=X)	Severe	x	x.x	x.x, x.x	x.x	x.x, x.x	
	Placebo (N=X)		x	x.x	x.x, x.x			
	Remdesivir (N=X)	Any Severity	x	x.x	x.x, x.x	x.x	x.x, x.x	
	Placebo (N=X)		x	x.x	x.x, x.x			

Repeat for the Treated Population.

N= Number of subjects in the specified treatment group, disease severity, and analysis population.

n = Number of recovered subjects.

HR for the ‘Any Severity’ group is the hazard ratio from the stratified Cox Model.

P-value calculated using the stratified log-rank test

Tables with similar format:

Table 15: Time to Recovery by Treatment Group and Disease Severity: Fine-Gray and Interaction Modeling

Table 16: Time to Recovery by Treatment Group within Subgroups – ITT Population

Table 17: Time to Recovery by Treatment Group within Subgroups – Treated Population

Table 18: Time to Recovery by Treatment Group and Disease Severity: Readmittance Sensitivity Analysis – ITT Population

Table 19: Time to Recovery by Treatment Group and Disease Severity: Concomitant Medication Sensitivity Analysis – ITT Population

Table 20: Time to Recovery by Treatment Group and Disease Severity: Unblinding and Crossover Treatment Sensitivity Analysis – ITT Population

Programming Notes for Table 15:

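### If the trial is not stopped early, SAP 8.1.1 reports the primary result as a fixed-sample 5% analysis, contradicting SAP 6.1 and not matching the Lan-DeMets final bound

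*SAP*

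**What the plan says.** SAP 6.1 sets the rule for intervals: "for the primary analysis, the confidence level will take into account the group-sequential design of the trial". It points to 6.6 and 8.1 for the method and keeps plain 95% intervals for secondary and exploratory outcomes. SAP 6.6.2 monitors the "primary endpoint using an overall two-sided type-I error rate of 0.05", with the O'Brien-Fleming-type Lan-DeMets spending function. SAP 6.8 repeats the commitment: "The study utilizes a group-sequential design to control the overall type I error rate". SAP 8.1.1 uses the same spending function "to maintain an overall two-sided type-I error rate of 0.05", and its pseudocode compares the final log-rank statistic with bounds updated for the observed information.

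SAP 8.1.1 then gives two reporting branches. If the trial stops at the interim, the p-value, median unbiased estimate and interval come from stage-wise ordering. Otherwise: "If the trial is not stopped early, then the fixed sample estimates of the statistics using an alpha level of 5% will be computed", and these are reported for both analysis sets. In the Table 14 shell the HR interval is headed 95%, and a footnote says the HR for the Any Severity "group is the hazard ratio from the stratified Cox Model". No adjusted level appears.

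On datasets, 8.1.1 says: "All the summaries described in this section will be generated for both the early and the full analysis sets". SAP 6.2.3 says: "The final analyses of all outcomes and planned summaries/listings will be performed on the final full locked database and provided in an addendum" to the report. SAP 4.1 still ties the primary analysis to the subjects enrolled to reach 400 recoveries.

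**The concern.** Section 8.1.1 holds two standards for the final primary result: a group-sequential bound, and a fixed-sample 5% p-value and interval. It does not say which governs. The second takes no account of the alpha spent at the interim. In the not-stopped branch the published interval could exclude 1, with p below 0.05, when the bound has not been crossed. That is also what 6.1 says will not be done.

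Two smaller gaps make this harder to settle. SAP version 3.0 was written after the DSMB review of April 27, 2020, and enrollment was permitted only until April 20. It is therefore unclear whether the trial counts as stopped at the interim, and the SAP does not say, although that choice selects the inference method. Both the early and the full set receive a primary p-value, and neither is ranked above the other.

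**Working it through.** **Inputs.**
- Overall two-sided alpha 0.05, built as two one-sided bounds at 0.025 (SAP 6.1, 6.6.2).
- One interim at about 50% information, with t = r/400 (SAP 6.6.2).
- 400 recoveries for a rate ratio of 1.35 at 85% power (SAP 5); 1:1 allocation (SAP 4.2.3).
- Recovery probability 70% (Protocol 9); total size 600 to over 800 (SAP 4.1).

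**Reproducing the plan's figures.** Spending per side is 2[1 − Φ(2.2414/√t)], and looks are correlated √(ti/tj). For the looks at 1/3, 2/3 and 1 in Protocol 9.4.6.2, the bounds come out at 3.710, 2.511 and 1.993. Protocol 9.4.6.1 prints 3.71, 2.51 and 1.99. The event formula gives 399 recoveries for a ratio of 1.35, against 400 stated.

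**SAP design, look at 200 of 400.**
- Spending at t = 0.5: 2[1 − Φ(2.2414/0.7071)] = 0.001525 per side, 0.00305 two-sided. Interim bound 2.963.
- Final bound b solves P(Z1 < 2.963, Z2 < b) = 0.975 with correlation √0.5. Result: b = 1.9686, nominal two-sided p 0.0490, matching interval level 95.1%.
- With the same interim and 1.960 at the end, overall two-sided alpha is 0.0510; with 1.9686 it is 0.0500.

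**Where the two rules disagree.** At 400 recoveries SE(log ratio) = 2/√400 = 0.1. The zone is |Z| from 1.960 to 1.9686, an observed ratio from exp(0.1960) = 1.2165 to exp(0.1969) = 1.2176. The chance of continuing past the interim and ending there is 0.1% under no effect (two-sided) and 0.2% at a true ratio of 1.35.

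Example at Z = 1.965 (log ratio 0.1965, p = 0.0494):
- 95%: exp(0.1965 ± 0.1960) = 1.0005 to 1.481, which excludes 1.
- 95.1%: exp(0.1965 ± 0.1969) = 0.9996 to 1.482, which does not.

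**Full analysis set.** The projected 600 to 800 subjects at 70% recovery give 420 to 560 recoveries. The interim is assumed to have been at 200 recoveries, with the remaining alpha spent at the end:

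| Final recoveries | Final bound | Overall alpha if 1.960 is used |
|---|---|---|
| 420 | 1.9694 | 0.0511 |
| 490 | 1.9718 | 0.0514 |
| 560 | 1.9736 | 0.0516 |

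**Sensitivity to the actual look.** The documents do not give the interim recovery count. For a final analysis at 400:

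| Interim fraction | Final bound | Overall alpha if 1.960 is used |
|---|---|---|
| 0.40 | 1.962 | 0.0503 |
| 0.50 | 1.969 | 0.0510 |
| 0.60 | 1.981 | 0.0523 |
| 0.67 | 1.994 | 0.0536 |
| 0.80 | 2.025 | 0.0561 |

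**The case against.** The strongest reply is that the decision rule is intact. SAP 8.1.1 compares the log-rank statistic with updated bounds, and the disputed sentence concerns only what is computed and reported. On that reading overall alpha is 0.05, and the 0.0510 to 0.0516 figures describe a test the SAP does not prescribe. This stands as far as it goes: the sentence does not prove an inflated decision rule. But the SAP never says that the bound alone decides or that the fixed-sample figures are descriptive. Section 6.1 governs the reported confidence level, so the contradiction remains even under the reporting-only reading.

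The practical effect is also close to nil. Under the rounding rules in SAP 13, both intervals in the example would print as 1.00 to 1.48, and both 0.0494 and 0.0490 as 0.049. That is correct, and it limits the severity. A plan written to spend alpha by actual information should still not discard that at the last step, and the gap grows if the look was later than planned.

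Two further points stand in part. SAP 17 allows shell formatting to change, so the Table 14 header is supporting evidence only. SAP 6.2.3 does label the full-database analysis as final, which gives some direction, but it stops short of naming that set decisive while both carry a primary p-value. The stopped branch does reflect the design and is not at issue.

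**Conclusion.** The point holds. As written, the not-stopped branch of SAP 8.1.1 contradicts SAP 6.1 on the primary interval and does not match the bound that keeps overall alpha at 0.05. At the planned look the discrepancy is 1.960 against 1.969 in the critical value, and 0.0510 against 0.0500 in overall alpha if 1.960 were used to decide. The size assumes a single look at 200 of 400 recoveries; the full-set figures of 0.0511 to 0.0516 also assume 420 to 560 final recoveries. A materially larger effect would need a later look, which the documents neither confirm nor exclude.

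It should be fixed because it concerns how the primary result is stated and the repair is nearly free. The unstated branch, the unranked analysis sets and the leftover 400-recovery text in SAP 4.1 are accurate observations, but they are requests for clarification and add no weight to this conclusion.

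**What to change.** Replace the not-stopped sentence in SAP 8.1.1. The primary p-value should be judged against the Lan-DeMets final bound computed from the actual interim and final information, with total two-sided spending of 0.05, and the interval level should be set by the same bound. For a look at 200 of 400 this means nominal p 0.0490 and a 95.1% interval. Head the HR interval in Table 14 with that level for the primary row.

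Declaring the fixed-sample figures descriptive and the bound decisive would settle the decision rule, but 6.1 would then have to be amended too.

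In the same revision, state which branch applies after the April 27 review, given the April 20 enrollment close. Name the early or the full set as decisive, report the other without a confirmatory p-value, and update the 400-recovery text in SAP 4.1. Separately, reconcile the 33%, 67% and 100% looks in Protocol 9.4.6.2 with the single look near 50% in SAP 2.1.

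Cost: wording and one table header. The interval widens by 0.4% on the log scale (1.9686/1.9600 = 1.0044). Power at 400 recoveries and a ratio of 1.35 has drift 10 × ln 1.35 = 3.001. It goes from Φ(3.001 − 1.960) = 85.1% to Φ(3.001 − 1.9686) = 84.9% on the final bound alone, or 85.0% over both looks.

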8.1.2. Supplemental and Sensitivity Analyses

For all supplemental and sensitivity analyses of the primary outcome, p-values will not be reported, and 95% confidence levels will be used for confidence interval estimates.

The primary analysis will be repeated in the Treated analysis population where subjects who are ineligible at baseline will be censored at enrollment. The tabular and graphical summaries described in the previous section will be replicated for this Treated analysis.

Sensitivity analyses will be performed using Cox proportional hazards models to estimate the hazard ratio. First, an ITT analysis will be performed in which subjects who die prior to recovering are treated as experiencing a competing risk in the Fine-Gray proportional hazards regression model. Second, a Cox model will be fit with binary indicators for treatment group and disease severity (Mild/Moderate vs. Severe [separate models for randomized stratum and actual stratum]) as well as a treatment * disease severity interaction term. The models will be fit to the ITT analysis population. The treatment group hazard ratios and CIs will be reported for both sets of models and the interaction term p-value will be reported for the interaction models.

The primary analysis will also be repeated using the other subgroups defined in Section 6.4 in place of disease severity. Each subgroup will be considered separately and the tabular and graphical summaries described in the previous section will be replicated for each subgroup. The tabular summary will also include results from an analysis of time to recovery controlling for age and duration of symptoms as continuous covariates. A forest plot will be generated to display the overall treatment hazard ratio estimate and CI from each of the within-stratum analyses (Figure 6). These analyses will be performed in the ITT and Treated populations.

In addition, a forest plot will be generated for the “leave one out” sensitivity analyses described in Section 6.7; hazard ratio estimates and CIs will be provided for each subgroup that leaves a single site out.

An additional sensitivity analysis will evaluate the effect of recoveries that were not sustained as indicated in Section 3.3.2.

As noted in Section 6.4, analyses that take into account concomitant medication will be performed. The primary analysis will be repeated, where subjects who take prohibited medications will be treated as treatment failures and will be censored at the time of medication use.

As noted in Section 3.3.2, an analysis of the primary outcome where placebo subjects has crossover treatment with remdesivir are censored at the time of retreatment will be performed. To support this sensitivity analysis, a summary of the clinical status scores assessed on the day of retreatment and the following day will be provided (Table 21). A spaghetti plot of the clinical status scores by study day will be provided for all placebo subjects, where the subjects who are retreated will be highlighted (Figure 9).

Two corroborative summaries will also be generated. A summary of the number and percentage of subjects in each treatment group who recovered (and are alive), did not recover (and are alive), and died by Day 29 will be summarized. The summary will also include the numbers and percentages, grouping deaths and non-recoveries together (Table 23). The summaries will also be provided by the duration of symptoms categorizations specified in Section 6.4.

Other censoring techniques and additional analyses of the primary outcome may be performed.

